8.2.2 REPORTING OF PREGNANCY AND LACTATION

Although pregnancy and lactation are not considered adverse events, it is the responsibility of investigators or their designees to report any pregnancy or lactation in a subject (spontaneously reported to them) that occurs during the trial or within 120 days of completing the trial or 30 days following cessation of treatment if the subject initiates new anticancer therapy, whichever is earlier. All subjects who become pregnant must be followed to the completion/termination of the pregnancy. Pregnancy outcomes of spontaneous abortion, missed abortion, benign hydatidiform mole, blighted ovum, fetal death, intrauterine death, miscarriage and stillbirth must be reported as serious events (Important Medical Events). If the pregnancy continues to term, the outcome (health of infant) must also be reported.

Such events must be reported within 24 hours to the principal investigator and Merck either by electronic media or paper.

8.2.3 IMMEDIATE REPORTING OF ADVERSE EVENTS

8.2.3.1 SERIOUS ADVERSE EVENTS

A serious adverse event is any adverse event occurring at any dose or during any use of pembrolizumab that:

- Results in death;
- Is life threatening;
- Results in persistent or significant disability/incapacity;
- Results in or prolongs an existing inpatient hospitalization;
- Is a congenital anomaly/birth defect;
- Is a new cancer (that is not a condition of the study);
- Is associated with an overdose;
- Is another important medical event

Refer to **Table 11** for additional details regarding each of the above criteria.

Progression of the cancer under study is not considered an adverse event unless it results in hospitalization or death.

Any serious adverse event, or follow up to a serious adverse event, including death due to any cause other than progression of the cancer under study (reference Section 7.2.3.3 for additional details) that occurs to any subject from the time the consent is signed through 90 days following cessation of treatment, or 30 days following cessation of treatment if the subject initiates new anticancer therapy, whichever is earlier, whether or not related to pembrolizumab, must be reported within 24 hours to the principal investigator and Merck either by electronic media or paper.

Additionally, any serious adverse event, considered by an investigator who is a qualified physician to be related to pembrolizumab that is brought to the attention of the investigator at any time outside of the time period specified in the previous paragraph also must be reported immediately to the principal investigator and Merck.

All subjects with serious adverse events must be followed up for outcome.

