irAEs are defined as an adverse event associated with pembrolizumab exposure and mediated through an immune mechanism. irAEs may be predicted based on the nature of the known mechanism of action of pembrolizumab, as well as experience with other immunotherapies with a similar mechanism of action. Special attention should be paid to AEs that are suggestive of potential irAEs. An irAE can occur shortly after the first dose, or several months after the final dose of pembrolizumab. If an irAE is suspected, effort should be made to rule out other potential etiologic causes prior to labeling an AE as an irAE. Information on how to identify and evaluate irAEs is included in the event of clinical interest and immune-related adverse event guidance document located in the administrative binder.

Events of clinical interest (ECI)

ECIs are non-serious and serious AEs that may or may not be irAEs. ECIs must be reported to Merck within 24 hours regardless of attribution to pembrolizumab.

Information on how to identify and report ECIs can be referenced in Section 8.2.3.2.

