6.8 SUBJECT WITHDRAWAL/DISCONTINUATION CRITERIA

Subjects may withdraw consent at any time for any reason or be removed from the trial at the discretion of the investigator should any untoward effect occur. In addition, a subject may be withdrawn by the investigator or the sponsor if enrollment into the trial is inappropriate, the trial plan is violated, or for administrative and/or other safety reasons.

A subject must be discontinued from the trial for any of the following reasons:

- The subject or legal representative (such as a parent or legal guardian) withdraws consent.

A subject must be discontinued from treatment (but may continue to be monitored in the trial) for any of the following reasons:

- The subject or legal representative withdraws consent for treatment
- Disease progression occurs
- Unacceptable AEs develop as described in Tables 5 and 6, and Sections 6.6.1.1 and 6.6.1.2
- Intercurrent illness develops that prevents further administration of pembrolizumab
- Investigator's decision
- The subject becomes pregnant
- The subject is non-compliant with the treatment or trial requirements

- The subject is lost to follow-up
- Administrative reasons

The end of treatment and follow-up visit procedures are listed in Section 7.0 (Trial flow chart) and Section 8.1.5 (Visit Requirements). After the end of treatment, each subject will be followed for 30 days for adverse event monitoring (serious adverse events will be collected for 90 days after the end of treatment). Subjects who discontinue for reasons other than progressive disease will have post-treatment follow-up for disease status until disease progression, initiating a non-study cancer treatment, withdrawing consent or becoming lost to follow-up. After documented disease progression or the start of new anti-cancer therapy, each subject will be followed by telephone for overall survival until death, withdrawal of consent, or the end of the study, whichever occurs first.

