7.6 CYCLE 34 – POST TREATMENT

Trial Period				
Weeks of treatment/cycle#	100(D1C34)	103(D1C35)	End of Treatment***	Post-Treatment***
Scheduling Window (days):	(+/- 3)	(+/- 3)	(+/- 7)	(+/- 7)
Administrative Procedures				
Informed Consent				
Inclusion/Exclusion Criteria				
Demographics and Medical History				
Prior and Concomitant Medication Review				
Trial Treatment Administration	X	X		
Post-Study anticancer therapy status				X
Survival status	X	X	X	X
Clinical Procedures/Assessments				
Review Adverse Events	X	X	X	X
Full Physical Examination				
Directed Physical Examination	X	X	X	X
Vital signs and Weight	X	X	X	X
ECOG Performance Status	X	X	X	X
Laboratory Procedures/Assessments: analysis performed by local laboratory				
Pregnancy Test- Urine or Serum b-HCG				
PT/INR and aPTT				
CBC with differential	X	X	X	X
Comprehensive Serum Chemistry Panel	X	X	X	X
Urinalysis				

Trial Period				
Weeks of treatment/cycle#	100(D1C34)	103(D1C35)	End of Treatment***	Post-Treatment***
Scheduling Window (days):	(+/- 3)	(+/- 3)	(+/- 7)	(+/- 7)
T3, FT4, and TSH	X		X	X
HIV, CMV				
HBV core antibody, anti-HCV antibody				
Peripheral blood chimerism				X
Efficacy Measurements				
Tumor Imaging*				X
BM Biopsy**				X
Tumor Biopsies/Archival Tissue Collection Correlative Studies Blood				
Archival or Newly Obtained Tissue Collection				X
Correlative Studies Blood Collection				X

*Tumor imaging only for HL and NHL

**BM biopsy only for AML, MDS patients. For HL and NHL patients, a bone marrow is required only in patients with a prior history of marrow involvement

***The safety visit (Section 8.1.6.3) can be completed on the same date as the initial end of treatment or post-treatment visit. Follow-up visits should occur every 12 weeks until initiation of a new anti-cancer therapy, disease progression, withdrawal of consent or death, whichever comes first.

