8.1.6.3 SAFETY FOLLOW-UP VISIT

The mandatory safety follow-up visit should be conducted approximately 30 days after the last dose of pembrolizumab treatment or before the initiation of a new anti-cancer treatment, whichever comes first. The safety follow-up visit can be done on the same day as the end of study visit (Section 8.1.6.2) or the end of treatment visit (Section 8.1.6.1). All AEs that occur prior to the safety follow-up visit should be recorded. Subjects with an AE of grade > 1 will be followed until the resolution of the AE to grade 0-1, or until the beginning of a new anti-cancer therapy, whichever occurs first. SAEs that occur within 90 days of the end of treatment or before initiation of a new anti-cancer treatment should also be followed and recorded.

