8.2.3.2 EVENTS OF CLINICAL INTEREST

Selected non-serious and serious adverse events are also known as Events of Clinical Interest (ECI) and must be recorded as such on the adverse event case report forms/worksheets and reported within 24 hours to the principal investigator and Merck

either by electronic media or paper.

Events of clinical interest for this trial include:

1. an overdose of pembrolizumab, as defined in Section 8.2.1, that is not associated with clinical symptoms or abnormal laboratory results.
2. an elevated AST or ALT lab value that is greater than or equal to 3X the upper limit of normal and an elevated total bilirubin lab value that is greater than or equal to 2X the upper limit of normal and, at the same time, an alkaline phosphatase lab value that is less than 2X the upper limit of normal, as determined by way of protocol-specified laboratory testing or unscheduled laboratory testing.*

*Note: These criteria are based upon available regulatory guidance documents. The purpose of the criteria is to specify a threshold of abnormal hepatic tests that may require an additional evaluation for an underlying etiology. The trial site guidance for assessment and follow up of these criteria can be found in the Investigator Trial File Binder (or equivalent).

3. Early transplant-related events such as veno-occlusive disease (VOD) and steroid-requiring febrile syndrome.

A separate guidance document has been provided entitled “Event of Clinical Interest Guidance Document.” This document can be found in the administrative binder and provides guidance regarding identification, evaluation and management of ECIs and irAEs.

ECIs identified in this guidance document from the date of first dose through 90 days following cessation of treatment, or 30 days after the initiation of a new anticancer therapy, whichever is earlier need to be reported to the SPONSOR within 24 hours of the event consistent with standard SAE reporting guidelines and either by electronic media or paper. Sponsor Contact information can be found in the administrative binder.

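### Once a patient starts new anticancer therapy, the SAE windows in 2.1/6.8, 8.1.6.3 and 8.2.3.1 conflict, the ECI window uses another anchor, and the 8.2.3.1 window can close before the DLT period ends

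*Combined protocol and SAP*

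**What the plan says.** Three rules govern SAEs after treatment ends.

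- **Sections 2.1 and 6.8:** "serious adverse events will be collected for 90 days after the end of treatment". Neither section shortens this for new therapy.
- **Section 8.1.6.3:** "SAEs that occur within 90 days of the end of treatment or before initiation of a new anti-cancer treatment should also be followed and recorded". It does not say whether the earlier or the later limit applies.
- **Section 8.2.3.1:** an SAE must be reported within 24 hours if it occurs between consent and a limit worded as "through 90 days following cessation of treatment, or 30 days following cessation of treatment if the subject initiates new anticancer therapy, whichever is earlier". The next paragraph adds that an SAE the investigator considers related to pembrolizumab, and learns of outside that period, must still be reported.

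A fourth rule covers ECIs. Section 8.2.3.2 makes the ECIs listed in a separate guidance document reportable from first dose "through 90 days following cessation of treatment, or 30 days after the initiation of a new anticancer therapy, whichever is earlier", and describes this as consistent with SAE reporting.

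Two other provisions bear on the point. Section 2.1 limits DLTs to the 90 days after pembrolizumab is started. In that definition, grade 3 or 4 acute GVHD and graft rejection count without any relatedness judgement. Section 6.6.1.1 warns about timing: "An irAE can occur shortly after the first dose, or several months after the final dose of pembrolizumab".

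**The concern.** Sections 8.2.3.1 and 8.2.3.2 both use 30 days, but the first counts from stopping study drug and the second from starting the next therapy. Neither agrees with the unconditional 90 days in 2.1 and 6.8. A site cannot apply all of these to one patient, so what is recorded after new therapy begins depends on which section it follows.

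Tolerability is the primary objective. Uneven capture makes late-event rates hard to interpret. If it reaches into the DLT period, it also affects the count on which the 9.1.3 interim decision rests, where fewer than 5 DLTs in 12 patients opens the expansion and 5 or more closes accrual.

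**Working it through.** No figure in the plan needs reproducing here, because the check only compares end dates.

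**Step 1. End date under each rule.** Let day 0 be the end of study treatment (taken as the last dose) and let new therapy start on day t, with t no later than 90.

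- 2.1 and 6.8: 90
- 8.1.6.3: min(90, t) if the earlier limit applies; max(90, t) = 90 if the wording is inclusive
- 8.2.3.1: min(90, 30) = 30
- 8.2.3.2 (ECIs): min(90, t + 30)

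| t | 2.1, 6.8 | 8.1.6.3, earlier | 8.1.6.3, inclusive | 8.2.3.1 | 8.2.3.2 (ECI) |
|---|---|---|---|---|---|
| 10 | 90 | 10 | 90 | 30 | 40 |
| 20 | 90 | 20 | 90 | 30 | 50 |
| 30 | 90 | 30 | 90 | 30 | 60 |
| 45 | 90 | 45 | 90 | 30 | 75 |
| 60 | 90 | 60 | 90 | 30 | 90 |
| 75 | 90 | 75 | 90 | 30 | 90 |

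With 8.1.6.3 read as the earlier limit, there are three distinct SAE end dates for every t from 1 to 89 except 30. Read inclusively, two remain, day 30 and day 90. At t = 10 the SAE spread is 90 − 10 = 80 days on the first reading and 90 − 30 = 60 days on the second.

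For t above 30, 8.2.3.1 taken literally ends before the event that triggers it. At t = 45 it closes on day 30, 15 days before the new therapy begins.

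**Step 2. An example.** New therapy starts on day 20 and an SAE judged unrelated occurs on day 40. It is collected under 2.1 and 6.8 and falls outside 8.2.3.1. It also falls outside 8.1.6.3 if the earlier limit applies. If it is also an ECI covered by 8.2.3.2, it is reportable there until day 50.

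**Step 3. Comparison with the DLT period.** On a 21-day schedule, doses 1 to 4 fall 0, 21, 42 and 63 days after first dose. If the patient stops and starts new therapy, the 8.2.3.1 window closes 30 days after the last dose given.

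| Doses received | Last dose (days after first dose) | 8.2.3.1 closes | Days short of 90 |
|---|---|---|---|
| 1 | 0 | 30 | 60 |
| 2 | 21 | 51 | 39 |
| 3 | 42 | 72 | 18 |
| 4 | 63 | 93 | none |

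After one to three doses the window therefore ends while a DLT can still occur. The provision for related SAEs does not fully cover this gap, because it needs a relatedness judgement that the GVHD and graft-rejection parts of the DLT definition do not require.

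**The case against.** The strongest reply is that nothing important goes missing. A reader might infer that a late GVHD or immune event is lost under one section and kept under another. For SAEs judged related the documents say otherwise, since 8.2.3.1 keeps them reportable whenever they come to the investigator's attention. Section 8.1.2.1 also has adverse events recorded during follow-up, and 8.3.1 requires all of them in routine data. This stands, and it confines the exposure to SAEs judged unrelated and non-serious ECIs. It does not remove the exposure. Table 11 guides the investigator to call an event related when pembrolizumab is the likelier cause, which is harder to judge once another therapy has started. Sections 8.1.1.5.3 and 8.1.6.4.1 then move the patient to telephone contact about survival only.

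A second reply is that the sections serve different purposes: 2.1, 6.8 and 8.1.6.3 concern collecting, following and recording, while 8.2.3.1 and 8.2.3.2 set 24-hour reporting. This explains part of the difference. It does not explain why 8.1.6.3 departs from 2.1 and 6.8, or why 8.2.3.1 and 8.2.3.2 count from different events.

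A reader might also infer four competing dates for any one event. Only three rules govern SAEs. GVHD is not named in the 8.2.3.2 list, so its ECI status rests on the grade 2 or higher immune-related text in 5.3 and on a guidance document outside these papers.

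Nor does 8.2.3.1 cancel reports already made. Its 30-day clause may have been meant for new therapy begun within the first 30 days, the case treated in 8.1.1.5.3, but it does not say so.

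Finally, a Table 5 footnote lets a patient with DLT-grade toxicity judged unrelated stay on trial. That concerns continuation and does not add a relatedness condition to the 2.1 definition.

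**Conclusion.** The inconsistency is real and worth correcting. After new therapy starts, the SAE windows differ by up to 60 days for new therapy on day 10 if 8.1.6.3 is inclusive, and by 80 days if its earlier limit applies. The ECI window ends on a date set by a different anchor. The consequence is uneven capture of SAEs judged unrelated and of non-serious ECIs, with weaker DLT ascertainment in patients who stop after one to three doses and go on to other therapy.

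This rests on four assumptions: cessation means the last dose; dosing is on schedule; 8.2.3.1 is read literally; and the 90-day limit in 2.1 applies to every part of the DLT definition, as 9.1.1 suggests for severe GVHD. The documents do not say how many patients will start new therapy early, so the number affected cannot be estimated and no effect on the interim decision is shown.

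**What to change.** Reconcile 2.1, 6.8, 8.1.6.3, 8.2.3.1 and 8.2.3.2 to one SAE window and one ECI window, both counted from the same event. If collection and 24-hour reporting are meant to differ, say so explicitly. State that collection of SAEs, GVHD and graft rejection runs at least to day 90 after first dose whether or not new therapy has started, and how the site will obtain that information. Record the start date of new therapy so that later events can be shown separately.

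The cost is protocol and case report form wording, plus some late event records confounded by the next therapy. Relative to 8.2.3.1, collection is extended by up to 60, 39 or 18 days for patients who stop after one, two or three doses. Sections 2.1 and 6.8 already promise SAE collection for at least that long.

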8.2.3.2 EVENTS OF CLINICAL INTEREST

Selected non-serious and serious adverse events are also known as Events of Clinical Interest (ECI) and must be recorded as such on the adverse event case report forms/worksheets and reported within 24 hours to the principal investigator and Merck

either by electronic media or paper.

Events of clinical interest for this trial include:

1. an overdose of pembrolizumab, as defined in Section 8.2.1, that is not associated with clinical symptoms or abnormal laboratory results.
2. an elevated AST or ALT lab value that is greater than or equal to 3X the upper limit of normal and an elevated total bilirubin lab value that is greater than or equal to 2X the upper limit of normal and, at the same time, an alkaline phosphatase lab value that is less than 2X the upper limit of normal, as determined by way of protocol-specified laboratory testing or unscheduled laboratory testing.*

*Note: These criteria are based upon available regulatory guidance documents. The purpose of the criteria is to specify a threshold of abnormal hepatic tests that may require an additional evaluation for an underlying etiology. The trial site guidance for assessment and follow up of these criteria can be found in the Investigator Trial File Binder (or equivalent).

3. Early transplant-related events such as veno-occlusive disease (VOD) and steroid-requiring febrile syndrome.

A separate guidance document has been provided entitled “Event of Clinical Interest Guidance Document.” This document can be found in the administrative binder and provides guidance regarding identification, evaluation and management of ECIs and irAEs.

ECIs identified in this guidance document from the date of first dose through 90 days following cessation of treatment, or 30 days after the initiation of a new anticancer therapy, whichever is earlier need to be reported to the SPONSOR within 24 hours of the event consistent with standard SAE reporting guidelines and either by electronic media or paper. Sponsor Contact information can be found in the administrative binder.

Subjects should be assessed for possible ECIs prior to each dose. Lab results should be evaluated and subjects should be asked for signs and symptoms suggestive of an immune-related event. Subjects who develop an ECI thought to be immune-related should have additional testing to rule out other etiologic causes. If lab results or symptoms indicate a possible immune-related ECI, then additional testing should be performed to rule out other etiologic causes. If no other cause is found, then it is assumed to be immune-related.

8.2.3.3 PROTOCOL-SPECIFIC EXCEPTIONS TO SERIOUS ADVERSE EVENT REPORTING

Efficacy endpoints as outlined in this section will not be reported as described in Section 8.2.3, unless there is evidence suggesting a causal relationship between the drug and the event. Any such event will be submitted to the principal investigator and Merck.

Specifically, the suspected/actual events covered in this exception include disease progression of the cancer during the study period.

The principal investigator will monitor aggregated efficacy endpoint events and safety data to ensure the safety of the subjects in the trial.

8.2.4 EVALUATING ADVERSE EVENTS

A qualified investigator will evaluate all adverse events according to the NCI Common Terminology for Adverse Events (CTCAE), version 4.0. Any adverse event which changes CTCAE grade over the course of a given episode will have each change of grade recorded on the adverse event case report forms/worksheets. All adverse events regardless of CTCAE grade must also be evaluated for seriousness.

Table 11. Evaluating adverse events

V4.0 CTCAE Grading	Grade 1	Mild; asymptomatic or mild symptoms; clinical or diagnostic observations only; intervention not indicated.
	Grade 2	Moderate; minimal, local or noninvasive intervention indicated; limiting age-appropriate instrumental ADL.
	Grade 3	Severe or medically significant but not immediately life-threatening; hospitalization or prolongation of hospitalization indicated; disabling; limiting self-care ADL.
	Grade 4	Life threatening consequences; urgent intervention indicated.
	Grade 5	Death related to AE
Seriousness	A serious adverse event is any adverse event occurring at any dose or during any use of pembrolizumab that:	
	†Results in death; or	
	† Is life threatening; or places the subject, in the view of the investigator, at immediate risk of death from the event as it occurred (Note: This does not include an adverse event that, had it occurred in a more severe form, might have caused death.); or	
	† Results in a persistent or significant disability/incapacity (substantial disruption of one's ability to conduct normal life functions); or	
	† Results in or prolongs an existing inpatient hospitalization (hospitalization is defined as an inpatient admission, regardless of length of stay, even if the hospitalization is a precautionary measure for continued observation. (Note: Hospitalization for an elective procedure to treat a pre-existing condition that has not worsened is not a serious adverse event. A pre-existing condition is a clinical condition that is diagnosed prior to the use of a Merck product and is documented in the patient's medical history.); or	

	
†Is a congenital anomaly/birth defect (in offspring of subject taking the product regardless of time to diagnosis);or
	
	
Is a new cancer; (that is not a condition of the study) or
	
	
Is an overdose (whether accidental or intentional). Any adverse event associated with an overdose is considered a serious adverse event. An overdose that is not associated with an adverse event is considered a non-serious event of clinical interest and must be reported within 24 hours.
	
	
Other important medical events that may not result in death, not be life threatening, or not require hospitalization may be considered a serious adverse event when, based upon appropriate medical judgment, the event may jeopardize the subject and may require medical or surgical intervention to prevent one of the outcomes listed previously (designated above by a †).
	
Duration	Record the start and stop dates of the adverse event. If less than 1 day, indicate the appropriate length of time and units	
Action taken	Did the adverse event cause pembrolizumab to be discontinued?	
Relationship to test drug	
Did pembrolizumab product cause the adverse event? The determination of the likelihood that pembrolizumab caused the adverse event will be provided by the investigator. The criteria below are intended as reference guidelines to assist the investigator in assessing the likelihood of a relationship between the test drug and the adverse event based upon the available information.
 
The following components are to be used to assess the relationship between pembrolizumab and the AE; the greater the correlation with the components and their respective elements (in number and/or intensity), the more likely pembrolizumab caused the adverse event (AE):
	
	Exposure	Is there evidence that the subject was actually exposed to pembrolizumab such as: reliable history, acceptable compliance assessment (pill count, diary, etc.), expected pharmacologic effect, or measurement of drug/metabolite in bodily specimen?
	Time Course	Did the AE follow in a reasonable temporal sequence from administration of pembrolizumab? Is the time of onset of the AE compatible with a drug-induced effect (applies to trials with investigational medicinal product)?
	Likely Cause	Is the AE not reasonably explained by another etiology such as underlying disease, other drug(s)/vaccine(s), or other host or environmental factors
Relationship	The following components are to be used to assess the relationship between the test drug and the AE: (continued)	
pembrolizumab (continued)	Dechallenge	Was pembrolizumab discontinued or dose/exposure/frequency reduced? If yes, did the AE resolve or improve?

		
If yes, this is a positive dechallenge. If no, this is a negative dechallenge.
 
(Note: This criterion is not applicable if: (1) the AE resulted in death or permanent disability; (2) the AE resolved/improved despite continuation of the Sponsor's product; or (3) the trial is a single-dose drug trial); or (4) Sponsor's product(s) is/are only used one time.)

	Rechallenge	
Was the subject re-exposed to pembrolizumab in this study?
 
If yes, did the AE recur or worsen?
 
If yes, this is a positive rechallenge. If no, this is a negative rechallenge.
 
(Note: This criterion is not applicable if: (1) the initial AE resulted in death or permanent disability, or (2) the trial is a single-dose drug trial); or (3) Sponsor's product(s) is/are used only one time).
 
NOTE: IF A RECHALLENGE IS PLANNED FOR AN ADVERSE EVENT WHICH WAS SERIOUS AND WHICH MAY HAVE BEEN CAUSED BY THE SPONSOR'S PRODUCT, OR IF REEXPOSURE TO PEMBROLIZUMAB POSES ADDITIONAL POTENTIAL SIGNIFICANT RISK TO THE SUBJECT, THEN THE RECHALLENGE MUST BE APPROVED IN ADVANCE BY THE PRINCIPAL INVESTIGATOR AS PER DOSE MODIFICATION GUIDELINES IN THE PROTOCOL.

	Consistency with Trial Treatment Profile	
Is the clinical/pathological presentation of the AE consistent with previous knowledge regarding pembrolizumab or drug class pharmacology or toxicology?

The assessment of relationship will be reported on the case report forms /worksheets by an investigator according to his/her best clinical judgment, including consideration of the above elements.
		
Record one of the following		
Use the following scale of criteria as guidance (not all criteria must be present to be indicative of pembrolizumab relationship).

Yes, there is a reasonable possibility of pembrolizumab relationship.		
There is evidence of exposure to pembrolizumab. The temporal sequence of the AE onset relative to the administration of pembrolizumab is reasonable. The AE is more likely explained by pembrolizumab than by another cause.

No, there is not a reasonable possibility of pembrolizumab relationship		
Subject did not receive pembrolizumab OR temporal sequence of the AE onset relative to administration of the pembrolizumab is not reasonable OR there is another obvious cause of the AE. (Also entered for a subject with overdose without an associated AE.)

